2.1.3 Exploratory Efficacy Objective

The exploratory efficacy objective for this study is to evaluate the efficacy of RO7234292 compared with placebo on the basis of the following endpoints:

- Change from baseline in the Apathy Evaluation Scale (AES) score at Week 101
- Change from baseline in the Symptoms of Major Depressive Disorder Scale (SMDDS) score at Week 101
- Change from baseline in the Huntington's Disease Daily Activities Scale (HD-DAS) score at Week 93
- Change from baseline in the Patient Global Impression, Severity Scale (PGI-S) score at Week 101
- Change from baseline in the Quality of Life in Neurological Disorders (Neuro-QoL) Cognition Function Short Form at Week 101
- Change from baseline in the Huntington's Disease Speaking Difficulty Item Scale (HD-SDI) score at Week 101
- Change from baseline in the Huntington's Disease Companion-Reported Irritability and Angry Outbursts Scale (HD-CIAOS) score at Week 101
- Change from baseline in the in-clinic patient-reported EuroQol 5-Dimension Questionnaire (5-level version; EQ-5D-5L) index-score and visual analogue scale (VAS) at Week 101
- Change from baseline in the sensor-based measures collected by the Roche HD mobile application (app; smartphone and wrist-worn wearable) at Week 101

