C-SSRS, neuroimaging assessments (neurologic safety sequences), and a review of any adverse events including related concomitant medications, as detailed in [Appendix 1a](#). Patients in Japan must be monitored in the hospital setting for at least 24 hours after Day 1 study drug administration. Discharge will be determined at the discretion of the principal investigator.

In the case of a failed IT bolus dosing procedure *or a failed CSF collection procedure* (e.g., due to an inadequate establishment of access to the IT space), a second attempt may occur up to 7 days after the originally scheduled attempt. For this additional visit, safety and tolerability evaluations on the day of LP administration will be performed as detailed in [Appendix 1a](#) and [Appendix 1b](#), including neurological examination (predose and postdose, *or pre-procedure if no study treatment is being administered*), vital signs, and a review of adverse events and concomitant medication. If the second attempt occurs more than 3 days after the first attempt, local laboratory analysis of coagulation factors (INR and/or PT, aPTT) and platelets need to be conducted again and results reviewed prior to the LP attempt (see [Appendix 1a](#)).

During the treatment period, a telephone safety follow-up call will be conducted for the months in which no clinic visits are scheduled to check for any change in patient status (i.e., adverse events, concomitant medications) since the patient's last visit (see [Appendix 1a](#)). Where deemed appropriate, an unscheduled clinic visit should be arranged for safety follow-up; no dosing will occur at these unscheduled visits. A safety follow-up telephone call will also be conducted approximately 2 months after the last in-clinic visit at Week 101.

Effective 22 March 2021, all patients will discontinue study treatment and will no longer be able to enter the OLE study (BN40955) after completing this study.

[figure not shown]
For patients enrolled in Study BN40423 who discontinue study treatment prematurely, but do not withdraw consent for continued participation in the study, an ETT schedule will apply (Section 3.1.1.1).

An iDMC and independent Data Coordinating Center (iDCC) will be employed to monitor and evaluate patient safety throughout the study as well as to evaluate evidence of early efficacy (see Section 3.1.2).

The Sponsor may choose to conduct one or more interim analyses during the study (further details are given in Section [6.12](#)).

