When applicable, study treatment administration will occur via a lumbar puncture using a needle inserted into the L3/L4 space, although placement at a different level (either in the space above or the space below) is allowed if patient anatomy or clinical judgment dictates. The left lateral position is mandatory in the first instance for the procedure for consistency of procedure practice across sites and within patients, unless patient-specific factors require use of the upright, sitting position or the physician/operator has pre-existing experience using LP/intrathecal bolus dosing in the sitting position and prefers the use of the upright sitting position, as guided by the patient, his or her judgment. Whichever position is used, once access is established to the IT space, the entire IT bolus procedure should be completed in the same position, to limit the risk of the needle losing position while the spinal needle is inserted. Subsequent LP administrations should occur using the same position.

Patients will be discouraged from resting supine after the lumbar puncture procedure and will be encouraged to mobilize immediately by walking around at a minimum and, if feasible, walking briskly for approximately 30 minutes, after which the postdose neurological examination can occur (*if study treatment was administered*). Patients should not perform any activity that is associated with a change in the ambient air pressure for at least 24 hours *post-LP procedure* (e.g., air travel, scuba diving, or hot air balloons).

Lumbar punctures will be performed as specified in the schedule of activities (see [Appendix 1](#)), with the last CSF sample obtained at the Week 101 end-of-treatment

visit. After discontinuation of study treatment, LPs will be performed at the ETT and EoT for ETT visits (see [Appendix 1a](#) and [Appendix 1b](#)). No study drug will be administered at these visits.

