4.5.9.23 Roche HD Mobile Application: Remote Testing (Smartphone and Wrist-Worn Wearable)

Smartphones and wrist-worn wearables have high-quality sensors that enable the remote, non-invasive, frequent, and precise measurement of motor and non-motor

symptoms (Maetzler et al. 2013; Andrzejewski et al. 2016; Adams et al. 2017; Lipsmeier et al. 2018). Each patient will receive a preconfigured smartphone and wrist-worn wearable with installed software for the Roche HD mobile app assessments. The devices and software will monitor motor symptoms, non-motor symptoms, and activities associated with routine daily living throughout the course of the study. Additional details are available in the Roche HD mobile app (Smartphone) manual.

Patients will be provided with devices and trained on their use during screening. Patients will also have in-clinic assessments of the digital platform that are supervised as indicated in [Appendix 7](#). Outside of the clinic, patients will be instructed to conduct an "active test" every day at approximately the same time (ideally in the morning, after breakfast). The active test consists of a short, preconfigured schedule of tasks that assess motor symptoms (upper and lower body movements, upper limb dexterity, voice) and non-motor symptoms (processing speed, voice). Testing will usually last approximately 5 minutes in total on a typical day of testing. Not all tests are daily. Additional information on the tasks and schedule is specified in [Appendix 7](#).

For "passive monitoring," patients will be instructed to carry the smartphone in a manner convenient to them (e.g., in a pocket or in a Sponsor-provided pouch) and wear the wrist-worn wearable throughout the day as they go about their daily routines.

Companions will receive their own independent electronic device at screening, which is different from the patient smartphone.

Patients will be encouraged to adhere to the daily schedule of tasks as much as possible; however, patients will not be excluded from the study for poor adherence, nor will missing a daily test be considered a protocol deviation.

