Device sensor data will be recorded continuously, throughout the active tests and passive monitoring. Sound will only be recorded during selected active test tasks. Data will be encrypted and uploaded to secure servers when the smartphone is connected to Wi-Fi. Patients will be asked to charge the devices overnight. If patients have a Wi-Fi network at home, they will be encouraged to connect their smartphone to enable data transfer. If no Wi-Fi network is available, the sensor data will be transferred during clinic visits or after the devices have been returned.

Roche HD mobile app "baseline" data will consist of all data collected prior to and including the baseline visit (up to 28 days). Baseline data will be collected for at least the 7 days up to and including Day 1.

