	Break (if needed)	~20–30	
2	Symbol Digit Modalities Test Stroop Word Reading Test MoCA	~20	Qualified study personnel
	Break (if needed)	~10	
3 ^a	Apathy Evaluation Scale (patient and companion) Symptoms of Major Depressive Disorder Scale	~20	Qualified study personnel
	Break (if needed)	~10–20	
4 ^a	Neuro-QoL Cognition Function Short Form EuroQol 5-Dimension, 5-Level Questionnaire (patient and companion) Health Utilities Index (companion: self and proxy) Patient/Companion-reported Global Impression—Severity Patient/Companion-reported Global Impression—Change (post-baseline visits only)	~20	Qualified study personnel
	Break (if needed)	~10–20	
5 ^a	Roche HD mobile application	~20	Qualified study personnel

HD=Huntington disease; MoCA=Montreal Cognitive Assessment; Neuro-QoL=Quality of Life in Neurological Disorders; UHDRS=Unified Huntington's Disease Rating Scale.

^a At the baseline visit and at Week 101, Blocks 3, 4, and 5 can be completed on the same day after Blocks 1 and 2, or on the following day, but must be completed predose at the baseline visit.

Appendix 4: Clinical Assessments Order and Duration for Patients Enrolled after Implementation of Protocol Version 4 (cont.)

Table 3 Follow-Up Clinical Assessments at Weeks 5, 21, 37, 53, 69, and 85

Block	Assessments	Total Duration (minutes)	Site Staff Responsible
1	UHDRS Functional Assessment Independence Scale Total Functional Capacity Scale Total Motor Score (without Diagnostic Confidence Level) Columbia-Suicide Severity Rating Scale Clinical Global Impression—Severity Clinical Global Impression—Change	~60	Qualified study physician
	Break (if needed)	~20-30	
2	Symbol Digit Modalities Test Stroop Word Reading Test MoCA	~20	Qualified study personnel
	Break (if needed)	~10	
3	Neuro-QoL Cognition Function Short Form EuroQol 5-Dimension, 5-Level Questionnaire (patient and companion) Health Utilities Index (companion: self and proxy) Patient/Companion-reported Global Impression—Severity Patient/Companion-reported Global Impression—Change	~30	Qualified study personnel
4	Roche HD mobile application ^a	~20	Qualified study personnel

MoCA=Montreal Cognitive Assessment; Neuro-QoL=Quality of Life in Neurological Disorders;
UHDRS=Unified Huntington's Disease Rating Scale

^a These assessments will take place only at Weeks 5 and 53.

Appendix 4: Clinical Assessments Order and Duration for Patients Enrolled after Implementation of Protocol Version 4 (cont.)

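### The digital baseline includes all of Day 1 with no predose cut, so passive sensor data recorded after the first injection count as baseline

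*Protocol*

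**What the plan says.** Section 4.5.9.23 fixes the baseline for the smartphone and wearable. Those baseline "data will consist of all data collected prior to and including the baseline visit (up to 28 days"), and the minimum is set in the next sentence: "Baseline data will be collected for at least the 7 days up to and including Day 1". The same section says: "Device sensor data will be recorded continuously, throughout the active tests and passive monitoring". For passive monitoring, patients carry the phone and "wear the wrist-worn wearable throughout the day as they go about their daily routines".

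Table 1 in Section 3.1.1 puts the first injection on Day 1 in all three arms. Section 4.5.5 says what follows a lumbar puncture: patients are encouraged to get moving at once, at least by walking around and, if feasible, by "walking briskly for approximately 30 minutes". Appendix 9 places the postdose neurological examination after 30 minutes of walking. Section 3.1.1 adds: "Patients in Japan must be monitored in the hospital setting for at least 24 hours after Day 1 study drug administration".

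Other baseline measurements are held to a predose rule. The notes to Appendix 1a require assessments on treatment days to precede dosing unless otherwise specified. Section 4.5.9 places in-clinic outcome data before the puncture. Appendix 4, Table 2, footnote a lets Blocks 3 to 5, of which Block 5 is the app test, move to the following day, "but must be completed predose at the baseline visit".

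Section 2.1.3 lists as an exploratory efficacy endpoint "Change from baseline in the sensor-based measures collected by the Roche HD mobile application" at Week 101.

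**The concern.** A baseline should describe the patient before treatment. As written, this one includes the hours after the first puncture and injection. Those hours are not the ordinary daily routine that passive monitoring is meant to capture. A prompted walk can raise recorded activity, and post-puncture symptoms can lower it. Section 5.1.1.1 reports headache after 10% of procedures in the Phase I/IIa study and allows for patients who find walking intolerable to sit or lie down.

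The weight of Day 1 also differs between patients, because the window runs from 7 to 28 days. Change from baseline in passive activity and movement measures would then start from a value that contains post-dose time in unequal proportions.

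**Working it through.** The plan gives no figure to reproduce, so the first check compares the texts.

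1. **End of the window.** Section 4.5.9.23 names Day 1 as included and sets no time of day.
2. **First exposure.** Table 1 gives Day 1 in every arm.
3. **Recording after the injection.** Sensors run continuously and the wearable is worn all day. Section 4.5.9.24 has patients bring both devices to every clinic visit, so the devices are present on Day 1.
4. **Reach of the predose rules.** The Appendix 1a note and Appendix 4 footnote govern assessments that are performed at a chosen time. Background recording is not performed in that sense. The Appendix 1a rule also yields where something else is specified, and Section 4.5.9.23 specifies Day 1.

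Steps 1 to 4 leave two kinds of data exposed: passive monitoring after the injection, and a remote active test done after it. The second should be uncommon, since Section 4.5.9.23 asks for the daily test ideally in the morning.

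The second check sizes the share, with each day weighted equally.

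- Inputs from Section 4.5.9.23: window length D = 7 days (minimum) or 28 days (maximum).
- Assumption: fraction f of Day 1 after dosing = 0.50 to 0.75.
- Assumption: wear time 10 to 16 hours per day.

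| Quantity | Formula | D = 7 | D = 28 |
|---|---|---|---|
| All of Day 1 | 1/D | 14.3% | 3.6% |
| Post-dose part, f = 0.50 | 0.50/D | 7.1% | 1.8% |
| Post-dose part, f = 0.75 | 0.75/D | 10.7% | 2.7% |
| 30-minute walk, 16 h wear | 0.5/(16 × D) | 0.4% | 0.1% |
| 30-minute walk, 10 h wear | 0.5/(10 × D) | 0.7% | 0.2% |

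The first row overstates the problem, because it includes the predose hours of Day 1. The next two rows measure the misclassified time. The walk by itself is under 1% of wear time.

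**The case against.** The strongest reply is that most of the digital data are already protected. The supervised app test must be predose, in-clinic data come before the puncture, and the remote active test is ideally done in the morning. Tapping, drawing, chorea, balance, U-turn and the electronic cognitive tests are therefore largely or wholly predose. This stands, and it confines the point to passive data and late remote tests.

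A second reply is that time-of-day cuts and valid-day rules for wearables belong in the SAP, which is not shown. That is true of such detail in general. Here, however, the protocol itself states the window and includes Day 1 in it, so an SAP that cut the data before the dose would depart from the protocol definition.

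Several stronger readings are tempting, and the protocol does not support them.

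- **A mandated brisk walk.** The walk is encouraged, and brisk only if feasible. Appendix 9 presupposes 30 minutes of walking but no pace.
- **A large distortion of walking measures.** Thirty extra minutes is 30/7 = 4.3 min/day over 7 days. Against an assumed habit of 15 to 60 min/day of brisk walking, that is 29% to 7%. The habit is assumed, the walk is taken as wholly additional, and Section 2.1.3 defines no such measure.
- **Bias between arms.** All three arms have the same puncture and injection. Only an acute drug effect on Day 1 could separate them.
- **Harm to the baseline covariate.** Section 6.6.5 plans summaries for exploratory endpoints and says only that modeling may be considered.
- **A mismatch with Week 101.** No Week 101 digital window is stated, so there is nothing to mismatch. Section 4.5.5 also schedules a puncture at that visit.
- **Regional noise from Japan.** Much of a 24-hour stay falls on Day 2, outside the window, and the number of patients in Japan is not given.

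**Conclusion.** The point holds in a limited form. Section 4.5.9.23 defines passive sensor data recorded after the first injection as baseline, and this conflicts with the predose principle applied to other baseline measurements. The misclassified share is about 7% to 11% of a 7-day window and 2% to 3% of a 28-day window. Those figures rest on the assumption that half to three quarters of Day 1 follows dosing and on equal weighting of days.

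The likely result is added noise and a shift common to all arms in the passive part of one exploratory endpoint. The direction of the shift is uncertain, since prompted walking and post-puncture symptoms act in opposite directions. The primary, secondary and safety analyses do not use these data. This is a minor correction, worth making because it costs almost nothing.

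**What to change.** Amend the baseline definition in Section 4.5.9.23 so that passive and remote app data end before the first dose. The simplest cut is the end of the day before the Day 1 visit, which needs no injection times. From the baseline visit, keep only the supervised predose app test. Restate the minimum to match: a patient with exactly 7 days through Day 1 would have 7 − 1 = 6 days under the new cut.

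Since no further study treatment is given, all Day 1 visits with dosing are past, and the change is one sentence plus a different data cut, with no new data. Section 3.1.2 says the Sponsor will be unblinded, so the cut should be documented before the sensor data are analyzed for efficacy. The cost is at most one baseline day per patient, which matters most for those near the 7-day minimum.

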4.5.9.24 Roche HD Mobile Application: In-Clinic Assessments

Patients will be instructed to bring the smartphone and wearable to every clinic visit to check adherence and technical status of the devices. At specified clinic visits, patients will be asked to conduct the "active test" tasks under the supervision of trained site staff, as shown in [Appendix 7](#).

The smartphone and wearable must be returned to the clinic in cases where the patient does not meet eligibility criteria, at the end of the study, or upon early termination from the study. At the time of study completion or early termination, patients will be asked to complete a pen-and-paper satisfaction survey about their experience using the smartphone and wrist-worn wearable.

4.5.10 Optional Samples for Research Biosample Repository

4.5.10.1 Overview of the Research Biosample Repository

The Research Biosample Repository (RBR) is a centrally administered group of facilities used for the long-term storage of human biological specimens, including body fluids, solid tissues, and derivatives thereof (e.g., DNA, RNA, proteins, peptides). The collection, storage, and analysis of RBR samples will facilitate the rational design of new pharmaceutical agents and the development of diagnostic tests, which may allow for individualized drug therapy for patients in the future.

Samples for the RBR will be collected from patients who give specific consent to participate in this optional research. RBR samples will be used to achieve the following objectives:

- To study the association of biomarkers with efficacy or disease progression
- To identify safety biomarkers that are associated with susceptibility to developing adverse events or can lead to improved adverse event monitoring or investigation
- To increase knowledge and understanding of disease biology and drug safety
- To study drug response, including drug effects and the processes of drug absorption and disposition
- To develop biomarker or diagnostic assays and establish the performance characteristics of these assays

4.5.10.2 Approval by the Institutional Review Board or Ethics Committee

Collection, storage, and analysis of RBR samples is contingent upon the review and approval of the exploratory research and the RBR portion of the Informed Consent Form by each site's IRB/EC and, if applicable, an appropriate regulatory body. If a site has not been granted approval for RBR sampling, this section of the protocol (Section 4.5.10) will not be applicable at that site.

4.5.10.3 Sample Collection

The following samples will be stored in the RBR and used for research purposes, including, but not limited to, research on biomarkers related to RO7234292, the HTT protein, HD or other diseases, or drug safety:

- Blood and serum samples collected at baseline and at Weeks 37, 69, and 101
- Leftover blood, plasma, and CSF samples and any derivatives thereof (e.g., proteins, peptides)

The above samples may be sent to one or more laboratories for analysis of germline or somatic mutations via whole genome sequencing (WGS), whole exome sequencing (WES), or other genomic analysis methods. Genomics is increasingly informing researchers' understanding of disease pathobiology. WGS and WES provide a comprehensive characterization of the genome and exome, respectively, and, along with clinical data collected in this study, may increase the opportunity for developing new therapeutic approaches or new methods for monitoring efficacy and safety or predicting which patients are more likely to respond to a drug or develop adverse events.

Data generated from RBR samples will be analyzed in the context of this study but will also be explored in aggregate with data from other studies. The availability of a larger dataset will assist in identification and characterization of important biomarkers and pathways to support future drug development.

For sampling procedures, storage conditions, and shipment instructions, see the laboratory manual.

RBR samples are to be stored until they are no longer needed or until they are exhausted. However, the RBR storage period will be in accordance with the IRB/EC-approved Informed Consent Form and applicable laws (e.g., health authority requirements).

4.5.10.4 Confidentiality

RBR samples and associated data will be labeled with a unique patient identification number.

Patient medical information associated with RBR samples is confidential and may be disclosed to third parties only as permitted by the Informed Consent Form (or separate authorization for use and disclosure of personal health information) signed by the patient, unless permitted or required by law.

Given the complexity and exploratory nature of the analyses of RBR samples, data derived from these analyses will generally not be provided to study investigators or patients unless required by law. The aggregate results of any conducted research will be available in accordance with the effective Sponsor policy on study data publication.

Data generated from RBR samples must be available for inspection upon request by representatives of national and local health authorities, and Sponsor monitors, representatives, and collaborators, as appropriate.

Any inventions and resulting patents, improvements, and/or know-how originating from the use of the RBR data will become and remain the exclusive and unburdened property of the Sponsor, except where agreed otherwise.

